8.4.3 Flow Cytometry Methods

Blood will be drawn into EDTA tubes and processed immediately on wet ice. Erythrocytes will be lysed with ammonium chloride buffer, and remaining leukocytes washed by centrifugation and suspended in protein free buffer for live dead labelling to allow for the elimination of false positives. Leukocytes will be transferred at 106 cells/100 μ L/test into tubes containing the following antibody cocktails and incubated for 30 minutes. Tubes will be simultaneously fixed and undergo secondary lysis with BD FACS lyse buffer which has the added benefit of allowing leukocyte cell populations to be identified using scatter profiles.

In Panel 1, antibodies targeting human CD91, CD14, CD16, HLADR, CD192 and CD197 will be used to determine changes in the circulating monocyte population. Neutrophils and monocytes mobilize intracellular stores of CD11b to the cell surface as they become activated, allowing a real-time measurement of systemic acute neutrophil and monocyte activation. Blood treated with a saturating amount of anti-human CD11b allowing for the quantitative analysis of expression to be reported as relative fluorescence intensity.

Systemic Blood Panel 1: CD11b acute activation and MO subtypes

Target	Channel	Vendor	Catalog#	Clone
CD11b	BL1-FITC	BioRAD	MCA551F	ICRF44
CD91	BL2-PE	ThermoFisher	12-0919-42	A2MR-a2
CD14	BL3-PerCP Cy5.5	BioRAD	MCA1568	Tük4
CD192	RL1-Alexa Fluor 647	BD Biosciences	558406	48607
CD16	RL3-APC H7	BD Biosciences	560195	3G8
CD197	VL1-BV421	BioLegend	353208	Go43H7
Live Dead	VL2-Fixable Aqua	ThermoFisher	L34966	NA
HLA-DR	V3-BV605,	BD Biosciences	562845	TU36

Using panel 2, platelet activation will be measured by the percentage of platelets associated with monocyte using the pan monocyte marker CD91 and the platelet membrane glycoprotein recognized by anti-human CD42a. Neutrophil life cycle will be evaluated using anti-human CD10, CD184 (CXCR4) and CD177. Immature neutrophils do not express CD10, while

CD177 and CD184 are expressed on aging neutrophils. A saturating amount of CD62L (L-selectin) will be used to allow for comparison of this activation marker across neutrophil subsets.

Systemic Blood Panel 2: CD62 on NE, monocyte platelet aggregates

Target	Channel	Vendor	Catalog#	Clone
CD62L	BL1-FITC	BD Biosciences	555543	DREG-56
CD91	BL2-PE	ThermoFisher	12-0919-42	A2MR-a2
CD10	BL3-PERCP Cy5.5	BD Biosciences	563508	HI10a
CD42a	RL1-Alexa Fluor 647	BioRAD	MCA1227A647	GRP-P
CD177	VL1-BV421	BD Biosciences	564240	MEM-166
Live Dead	VL2-Fixable Aqua	ThermoFisher	L34966	NA

Events will be collected using the ThermoFisher Attune flow cytometer and data analyzed using FlowJo software. Gates will be confirmed using fluorescence minus one controls, and a blue laser control bead will be used to ensure inter assay consistency with CD11b and CD62L that will be expressed as relative fluorescence in the blue laser line. Specificity of the antibodies will be confirmed using matched isotype controls. Statistical significance of differences in population percentages and relative fluorescence intensity values will be determined using Anova for repeated measures and paired student t test where appropriate.

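### Section 8.4.3 expresses platelet activation as a percentage of platelets in a washed leukocyte sample, so the value also depends on wash recovery and cell ratios; the parent gate should be CD91+ monocytes

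*Combined protocol and SAP*

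**What the plan says.** Section 8.4.3 of the combined protocol and SAP describes one preparation for both antibody panels. Red cells are lysed and the "remaining leukocytes washed by centrifugation and suspended in protein free buffer for live dead labelling". The tubes are then filled by leukocyte number: "Leukocytes will be transferred at 106 cells/100" µL per test (the figure is probably a power of ten whose superscript was lost in text extraction). A later fixation and lysis step is credited with "allowing leukocyte cell populations to be identified using scatter profiles".

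For Panel 2, "platelet activation will be measured by the percentage of platelets associated with monocyte using the pan monocyte marker CD91" together with "the platelet membrane glycoprotein recognized by anti-human CD42a". The table for that panel is headed "Systemic Blood Panel 2: CD62 on NE, monocyte platelet aggregates".

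The section closes with the test: "Statistical significance of differences in population percentages and relative fluorescence intensity values will be determined using Anova for repeated measures", or a paired t test where appropriate. It does not name the parent population for any percentage.

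**The concern.** The sentence defining the readout and the preparation that feeds it do not fit together. A percentage of platelets needs a platelet population that represents the patient's circulating platelets. This preparation is built to keep leukocytes. Free platelets remaining in the tube are a residue of the wash, and nothing in the section measures or controls that residue.

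The panel heading points to a different quantity, the share of monocytes that carry platelets. Two analysts working from the same section could therefore report two different percentages, and the choice could be made after the data are seen. If the written sentence is followed, a difference between the heparin session and the SCD session could reflect wash recovery, a change in monocyte count or a change in platelet count, and be read as a change in platelet activation.

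**Working it through.** The plan states no figure for this readout, so there is none to reproduce. The check has two parts.

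**1. The text of Section 8.4.3, side by side**

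- Definition sentence: the denominator is platelets.
- Preparation: lysis, centrifugal wash, loading by leukocyte number. No platelet-preserving step is given.
- Gating: scatter is described for leukocyte populations only. No platelet gate is given.
- Controls: the bead control is for CD11b and CD62L on the blue laser. CD42a is read on a red channel (RL1), so that control does not cover it, and it would not measure platelet recovery in any case.
- Heading: monocyte-platelet aggregates, with CD91 described as the pan-monocyte marker. This points to monocytes as the denominator.

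The definition sentence is the outlier.

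**2. Sensitivity of the two readouts**

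All inputs are assumptions, because the documents give none for this readout:

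- monocytes M = 500/µL
- platelets P = 200,000/µL
- share of monocytes carrying platelets f = 20%
- platelets per positive monocyte k = 1.5
- recovery of free platelets in the wash r from 100% down to 0.1%, with all monocytes retained

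Formulas, counting each platelet-bearing monocyte as one event:

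- As written: W = Mf / [Mf + r(P − kMf)]
- Monocyte-based: A = Mf / M = f

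With f = 20%, Mf = 100 and kMf = 150, so free platelets before the wash are 199,850/µL.

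| Free-platelet recovery r | W = 100 / (100 + 199,850 r) | A |
|---|---|---|
| 100% | 0.05% | 20% |
| 10% | 0.50% | 20% |
| 1% | 4.8% | 20% |
| 0.1% | 33% | 20% |

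Across this assumed range W changes about 670-fold (33.35 / 0.050) while the share of platelet-bearing monocytes is constant.

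Next, hold recovery at 10% and vary f:

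- f = 10%: 50 / (50 + 0.1 × 199,925) = 0.25%
- f = 20%: 100 / (100 + 0.1 × 199,850) = 0.50%
- f = 40%: 200 / (200 + 0.1 × 199,700) = 0.99%

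So W does respond to aggregate formation when recovery is constant.

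M and f enter W only as the product Mf. Halving the monocyte count to 250/µL with f unchanged at 20% gives Mf = 50 and W = 0.25%, the same as halving f to 10% at 500/µL. The written readout cannot tell fewer monocytes from fewer platelet-bearing monocytes.

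**The case against.** The strongest reply is that this is a slip of wording. The heading, the pan-monocyte marker and the leukocyte gating all indicate that the laboratory means the percentage of CD91+ monocytes carrying CD42a. Gating is done in software after acquisition, so nothing is lost if the definition is corrected later. Much of that stands, and it is why the point is minor. It does not remove the problem: the only sentence defining the readout gives the wrong denominator, and the section submits population percentages to significance tests without naming a parent gate.

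A second reply is that each patient is his or her own control and one preparation protocol is used throughout, so recovery may be fairly stable. That is possible; the documents give no data either way. Pairing does not guarantee it. Each patient gives six flow samples (before, at 5 hours and at 24 hours, in two sessions), and each is prepared separately.

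A reader might infer two stronger claims, and the documents support neither.

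- *That the written value does not track activation at all.* At constant recovery it rises almost in proportion to the share of platelet-bearing monocytes, as shown above.
- *That the written value favours the SCD because the device holds monocytes.* The mechanism text in Section 1 and Section 6.3.1 say that bound leukocytes are released back to the circulation. The pilot ESRD trial described in Section 1 reports no decline in total white cells, neutrophils or platelets. It gives no separate monocyte trend, so a fall is not excluded, but none is shown.

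The monocyte-based percentage stays at 20% in the illustration by construction. It is protected from loss of free platelets and from non-selective loss of monocytes. It is not protected if platelet-bearing monocytes are removed selectively.

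**Conclusion.** The point holds as a misdefined exploratory readout. Taken as written, the percentage has as its denominator the CD42a+ events left after a wash designed for leukocytes. It therefore mixes aggregate formation with wash recovery and the monocyte-to-platelet ratio, and it conflicts with the panel heading. This rests on the text of Section 8.4.3 alone.

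The size of the error in this trial is unknown. The range from 0.05% to 33% rests on assumed counts and recoveries. It shows sensitivity and does not estimate variation between sessions. No direction of bias is established.

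Severity is minor. The Study Synopsis and Section 8.12 list flow cytometry as exploratory, and neither names platelet activation. The correlations planned in Section 9 do not name it either. The primary outcome, the sample size and safety are unaffected.

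**What to change.** In Section 8.4.3, replace the definition for Panel 2 with: *Platelet activation will be measured as the percentage of live CD91+ monocytes that are CD42a+ (monocyte-platelet aggregates).* State that this percentage is the one used in the planned comparison of population percentages at the end of the section.

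The cost is one sentence. CD91, CD42a and the live/dead stain are already in Panel 2, so tubes, antibodies and recorded events stay the same and only the parent gate changes. The change should be made before the flow data are analysed.

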Since treatment of traditional risk factors for CVD have been ineffective, focus on non-traditional risk factors, especially acute and chronic inflammation, has become a focus of therapeutic interventions in dialysis patients. In this regard, inflammation and its cellular immunologic effector, the activated monocytes (MO), are central to the accelerated progression of CVD in patients with CKD and patients with ESRD on HD. Consequently, a focus on non-traditional and non-modifiable risk factors has emerged with MO activation as a prime therapeutic target. A pivotal pathobiologic role of MO and macrophages (Mφ) on development and progression of atherosclerosis has been clearly established⁸⁻¹⁰. In this regard, heterogeneous subpopulations of MO have been identified in humans. Cell surface expression of CD14 and CD16 identifies 3 functionally distinct subsets of MO: classical (CD14^{hi}, CD16⁻, pro-inflammatory), intermediate (CD14^{hi}, CD16⁺, pro-inflammatory) and non-classical (CD14^{low}, CD16⁺⁺, anti-inflammatory/reparative). Intermediate MO play an instrumental role in the development of atherosclerosis in the general and CKD populations¹¹⁻¹⁴. This subset of M has a greater degree of pro-inflammatory phenotype compared to the other subsets. Furthermore, epidemiologic studies have reported that the number of intermediate MO increases with worsening renal function and higher cell numbers predict adverse cardiovascular outcomes in ESRD patients undergoing chronic dialysis¹⁴⁻¹⁷. This proposal plans to evaluate a novel immuno-modulatory device, the selective cytopheretic device (SCD), on the immune dysregulated state of ESRD and to assess the benefit of this innovative strategy to improve cardiac performance and reduce progressive congestive heart failure (CHF).

The SCD has shown to improve clinical outcomes of critically ill patients with multiorgan dysfunction (MOD) by mitigating the inflammatory cascade. Benefit has also

been indicated with chronic inflammation, such as that observed in end stage renal disease (ESRD). This technology has proven to be effective in pre-clinical animal models of disease for which inflammation is present, such as cardiopulmonary bypass (CPB), septic shock and stroke. This proposal plans to further evaluate therapeutic impact of a novel device (SCD) specifically toward ischemic cardiac events during hemodialysis (HD) in ESRD patients.

SCD Mechanism of Action

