5mg/L were enrolled to assess the safety and early efficacy signals on inflammatory biomarkers in these patients. After a Non-Significant Risk designation by the Henry Ford Health System (HFHS) IRB, this study was performed ²¹. The clinical results demonstrated an excellent safety profile with no decline in total WBC, NE or platelet counts. To evaluate the effect of SCD therapy on M phenotypes in these patients, determination of CD14^{hi} fluorescent intensity on peripheral blood M was analyzed utilizing flow cytometry. SCD therapy promoted a shift in MO phenotype from predominantly CD14^{hi} expressing MO at baseline/pre-SCD therapy to CD14^{low} expressing MO post-SCD therapy (Figure 4, A/B). In the 13 ESRD patients evaluated, a significant shift in MO population phenotype afforded by a single SCD therapy session was observed ($p<0.013$). In a subset of patients ($n=7$) presenting with T2D, indicative of an even greater chronic inflammatory state, this persistent decline in M CD14 expression was sustained as long as 2 weeks post therapy (Figure 4, C). The average number of cells bound to the SCD membrane following 4 hours of therapy showed 1.13×10^9 , with 68% identified as NE, 23% M, 7% eosinophils and 0% lymphocytes. The eluted M were almost all of CD14^{high} phenotype; with the differential percentage being more than double the average 9% circulating M pool. Of note, two patients underwent SCD treatment with standard heparin HD (SHH), as opposed to RCA. No change in M phenotype was observed, but symptomatic and biochemical adverse events were seen after SHH+SCD treatment, including a greater than doubling of CRP levels. No further studies were undertaken with SHH+SCD treatment due to these adverse events.

Myocardial stunning in ESRD patients undergoing chronic hemodialysis

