8.3.1.40 Perform 2 D echo

8.3.1.41 Obtain blood for systemic soluble markers according to instructions in **Appendix 2**.

8.3.1.42 Obtain blood for flow cytometry according to instructions in **Appendix 2**.

Before Initiation of SCD Treatment

8.3.1.43 The PI must review all safety data of the Subject and determine their suitability to move to the SCD treatment. Further, the WBC count must be $>4000/\text{mm}^3$, neutrophil count >500 and platelet count $>50,000/\text{mm}^3$ in prior treatments.

Ionized calcium during SCD Treatment

8.3.1.44 The PI may draw more frequent iCa using i-STAT device if deemed necessary for safety concerns.

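### Leukocyte subsets are tested only as percentages and fluorescence, which cannot separate removal of CD14-high monocytes from a phenotype change, and the 24 h step list omits the scheduled CBC

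*Combined protocol and SAP*

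**What the plan says.** Section 8.4.3 (Flow Cytometry Methods) names two kinds of quantity for testing: "Statistical significance of differences in population percentages and relative fluorescence intensity values will be determined using Anova for repeated measures", or a paired t-test where suitable. No section defines or tests an absolute subset count. Section 9 plans correlations that involve monocyte subsets but gives no unit.

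The assay as described does not yield a concentration. Each tube receives a fixed number of cells ("Leukocytes will be transferred at 106 cells/100", where an exponent has probably been lost in text extraction). The only bead mentioned is for fluorescence: "a blue laser control bead will be used to ensure inter assay consistency with CD11b and CD62L". A count per mm³ can therefore come only from combining the flow percentage with the CBC.

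Section 1 argues along two lines. One is prognostic and concerns numbers: "the number of intermediate MO increases with worsening renal function and higher cell numbers predict adverse cardiovascular outcomes". The other is the device's own evidence from the ESRD pilot, which concerns phenotype: "a significant shift in MO population phenotype afforded by a single SCD therapy session was observed". The same pilot account reports the cartridge load. "The average number of cells bound to the SCD membrane following 4 hours of therapy" is given as 1.13 × 10⁹, "with 68% identified as NE, 23% M, 7% eosinophils and 0% lymphocytes", and the eluted monocytes were nearly all CD14-high.

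Section 8.3.1 includes a CBC with differential before treatment (8.3.1.12) and at 5 h (8.3.1.28). The 24 h list (8.3.1.40 to 8.3.1.42) contains an echocardiogram, soluble markers and the step beginning "Obtain blood for flow cytometry according to instructions in". It contains no CBC. Appendix 1 marks three CBCs per session, and Appendix 2 allows 3 mL per CBC and 18 mL in total.

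**The concern.** Subset percentages within a cell population must sum to 100. If the cartridge takes CD14-high monocytes out of the blood, the CD14-low percentage rises even though the number of CD14-low cells is unchanged and no cell has altered. Fluorescence values are not tied to a sum in this way. A population average of an activation marker would still fall if the device held the brighter cells. The heparin session has no SCD in the circuit, so comparing sessions within a patient does not cancel this effect.

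The 5 h sample is taken before the circuit is disassembled, when the bound cells are still on the membrane. The trial could then describe as a less inflammatory phenotype something that is partly or wholly retention in the device.

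The CBC is what would allow the two explanations to be told apart. If staff worked from the 24 h step list alone, it would be missing at the only scheduled time point after the patient has left the circuit. WBC and platelet recovery after SCD would also go unrecorded.

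**Working it through.** **CBC draws.** Appendix 2 gives 18 mL ÷ 3 mL = 6 draws, which is three per session over two sessions.

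- Appendix 1 (pre-treatment, 5 h, 24 h): 3 mL × 3 × 2 = 18 mL, which reproduces the stated total.
- Step list in 8.3.1 (pre-treatment, 5 h): 3 mL × 2 × 2 = 12 mL, which does not.
- Cross-check on tests drawn three times per session: flow cytometry 6 ÷ 1 = 6 draws; soluble markers 66 ÷ 11 = 6 draws.
- Cross-check on a test drawn twice per session: basic metabolic panel 8 ÷ 2 = 4 draws.

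The appendices agree with each other, and the step list is the outlier. The screening CBC is a review of existing results and uses no study blood.

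**Size of the retention effect.** Inputs from the pilot account in section 1 are 1.13 × 10⁹ bound cells, 23% of them monocytes, and 9% monocytes in circulation. The lower WBC of 4,000/mm³ is the eligibility floor. The upper WBC of 10,000/mm³, the blood volume of 4 to 6 L and a starting CD14-low share of 10% are assumptions. So are these: all bound monocytes are CD14-high, none are replaced, and the pilot load carries over.

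- Bound monocytes: 0.23 × 1.13 × 10⁹ = 2.6 × 10⁸.
- Circulating pool = blood volume × WBC × 0.09.
- Bound share f = bound ÷ pool.
- Relative rise in the CD14-low share = 1/(1 − f) − 1.

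| Blood volume, WBC | Monocyte pool | f | Relative rise | CD14-low share |
|---|---|---|---|---|
| 4 L, 4,000/mm³ | 1.44 × 10⁹ | 18.0% | 22.0% | 10% → 12.2% |
| 5 L, 6,000/mm³ | 2.70 × 10⁹ | 9.6% | 10.7% | 10% → 11.1% |
| 6 L, 10,000/mm³ | 5.40 × 10⁹ | 4.8% | 5.1% | 10% → 10.5% |

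The CD14-low count is unchanged in every row.

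**Why counts need correction.** Ultrafiltration concentrates the blood by 5 h. An assumed 5%, 10% or 15% fall in blood volume multiplies every count by 1/0.95, 1/0.90 or 1/0.85, a rise of 5.3%, 11.1% or 17.6%.

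Take the middle row. CD14-high cells fall from 90 to 80.4 per 100 starting monocytes, a ratio of 0.893, and CD14-low stays at 1.00. With a 5.3% concentration the observed ratios become 0.893 × 1.053 = 0.940 and 1.053. One subset appears to fall and the other to rise, yet no cell has converted. This happens for any concentration below 1/0.893 − 1 = 12%. Multiplying the 5 h count by pre-treatment hemoglobin ÷ 5 h hemoglobin restores 0.893 and 1.00, if red cell mass is unchanged.

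**The case against.** Four replies have force.

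1. **The 24 h CBC is already planned.** Appendix 1 schedules it, Appendix 2 budgets it and section 8.3 refers the reader to Appendix 1. The synopsis calls for all Appendix 1 procedures in the heparin session, and 8.3.1 requires the same procedures in both. A reader might infer from the step list that the test is absent from the plan. The documents do not support that. What stands is a conflict between two lists.

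2. **The device hypothesis is about phenotype.** Percentages and fluorescence match the pilot readout, and percentages are immune to hemoconcentration. A reader might infer from the prognostic sentence in section 1 that counts should replace percentages as the main measure. That sentence is only part of the rationale, and uncorrected counts would exchange one bias for another. This reply stands: counts belong beside percentages.

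3. **The pilot argues against retention as the whole story.** Bound cells are described as released, total WBC and neutrophils did not fall, and lower CD14 expression lasted up to 2 weeks in a subset of 7. Cells left on a discarded cartridge do not readily explain the last finding. Against this, 1.13 × 10⁹ is the number still bound after 4 h, so earlier release is already netted out. Over the same assumed ranges the bound cells are only 1.9% to 7.1% of all leukocytes, and no monocyte count is reported. The reply weakens the concern without removing it.

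4. **Counts could be computed later.** The CBC is drawn with the flow sample before treatment and at 5 h, and is scheduled at 24 h. This is true, and it is why the change is cheap. It does not make the count a planned analysis.

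**Conclusion.** The point holds as a minor one. Section 8.4.3 as written cannot distinguish loss of CD14-high monocytes from a change in phenotype, and the 24 h step list contradicts Appendices 1 and 2.

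The relative rise of 5% to 22% in the CD14-low share is an upper-end illustration. It rests on assumed blood volume, an assumed upper WBC, no replacement of bound cells and exclusive binding of CD14-high monocytes. In absolute terms it is 0.5 to 2.2 points on a share of 10%. The documents give no assay or patient variability to compare this with, so materiality is not established.

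A reader might go further and infer that the pilot's phenotype shift was an artefact, or that this trial's will be. The documents do not show that. They show only that the planned tests could not exclude it. Flow cytometry is an exploratory measurement in a study of 10 patients, and the primary outcome does not depend on it.

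**What to change.** 1. In section 8.4.3, keep the percentages and relative fluorescence and add absolute subset counts (CBC monocyte or neutrophil count × the flow percentage of that population). State the denominator of each percentage. Correct the 5 h and 24 h counts for hemoconcentration with the hemoglobin or hematocrit from the same CBC, and compare the corrected change with that in the heparin session. Describe a percentage change as a phenotype shift only if the corrected counts do not show it to be loss of CD14-high cells alone. In section 9, say which form of the subset measure enters the correlations.

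2. In the 24 h steps of section 8.3.1, add the CBC with differential and platelets, as already written for pre-treatment and 5 h, so that the list matches Appendices 1 and 2.

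The cost is two text edits and a small amount of extra analysis on exploratory measures. Blood use rises from the 12 mL implied by the step list to the 18 mL already in Appendix 2, so there is no draw beyond the budget.
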